6.1.6 Storage Conditions

Medications will be stored at room temperature 68-77 degrees Fahrenheit and away from heat, moisture and light. The shelf life of stored medication is 12 months. The pharmacist will send medications in batches such that medication will be available at the time of patients starting the study but not stored for so long that the shelf life expires.

Upon returning for routing post in vitro fertilization visit, all used and unused bottles will be returned to the study personnel to assess for patient compliance. The amount of study drug dispensed and returned by the subject will be recorded. The study monitor will verify these documents throughout the course of the study.

6.1.7 Concomitant therapy

As discussed above, aside from study medication (placebo versus letrozole) and blinding of providers to estradiol levels, all patients will receive the standard ovarian hyperstimulation protocol prescribed by their primary provider at the University of California Center for Reproductive Health.

6.1.8 Restrictions

See exclusion criteria and risks above.

6.2 Assessments

Endometriosis associated symptoms will be evaluated using a survey modeled after the clinical survey developed by the World Endometriosis Research Foundation Endometriosis Phenome and Biobanking Harmonisation Project [10]. The survey will use a visual analog scale (VAS) to quantify pain and symptoms experienced by participants. Participants will complete this survey at their baseline ultrasound appointment for their controlled ovarian hyperstimulation cycle, the day of trigger shot, 3 weeks following egg retrieval, 6 weeks following egg retrieval and 12 weeks following egg retrieval if not pregnant. The first survey will include questions regarding any recent or prior medical or surgical treatment of their

endometriosis. It will also assess baseline use of pain medications for their endometriosis-associated pain. Study participants will be allowed to take acetaminophen when needed (Tylenol, 650 mg tablet) for pain control, but asked to record the number of tablets used.

Secondary outcomes looking at egg and embryo quality and quantity will be assessed using standard embryologists evaluation and grading of all eggs and embryos collected during controlled ovarian hyperstimulation at the University of California Center for Reproductive Health. Embryologist will be blinded to the study participants' assignments to either placebo or control group.

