5.2.1 Primary Outcome Variables

- To compare the mean endometriosis pain score at baseline, 6 and 12 weeks following egg retrieval.
- To evaluate how endometriosis pain scores change throughout controlled ovarian hyperstimulation.

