6.3.1 Study Schedule

M.D. Visit	
 • M.D. to identify patient as potential study participant • M.D. discusses study with patient • M.D. to notify study team if patient interested
Meet Study Team	
 • Discuss study with patient and answer questions • Subject signs study and HIPPA consents • Randomization completed, patient provided medication
Baseline Ultrasound	
 • Completion of survey #1
Stimulation Monitoring	
 • Daily letrozole/placebo starting with first day of stimulation medications • Routine uterine and ovarian ultrasound monitoring every 1-3 days at UCSF CRH • Routine blood draws for hormonal assessment every 1-3 days at UCSF CRH (patients and providers blinded to estradiol levels)
Trigger Shot	
 • Based on routine trigger shot parameters, including mean diameter of largest follicles • Completion of survey #2 • Discontinuation of letrozole/placebo
Oocyte Retrieval	
 • Retrieve all visible follicles • Follicular fluid obtained for hormonal evaluation • Restart letrozole/placebo evening of retrieval and continue daily for 2 weeks
Embryology Lab	
 • Count total number of retrieved oocytes • Count mature oocytes and fertilization rate (if making embryos) • Assess embryo quality using UCSF CRH standard grading criteria

3 Weeks Post Retrieval	
 Completion of survey #3
6 Weeks Post Retrieval	
 Completion of survey #4
12 Weeks Post Retrieval	
 Evaluation of pregnancy status Completion of survey #5
Long-term Follow-up	
 Medical record review for pregnancy outcomes of transferred embryos and additional endometriosis treatment.

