At 3- 6- and 12-weeks post retrieval, participants will be contacted by phone and reminded to complete survey number 3, 4 and 5 respectively. These surveys will be completed at home electronically via a secure RedCap portal.

Long Term Follow Up:

After completion of survey 5 participants will not be contacted again about the study. Their chart will be periodically reviewed to assess pregnancy outcomes from the controlled ovarian hyperstimulation cycle. Treatments they receive related to their diagnosis of endometriosis will also be reviewed.

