6.4.1 Statistical Design

An intention-to-treat analysis of the results will be used, meaning results of the study will be based on the initial treatment assignment and not the treatment eventually received. The primary outcome will be assessed by changes in pain survey scores before, during and following controlled ovarian hyperstimulation.

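### The 6- and 12-week pain scores are dated only from egg retrieval, so a randomised woman whose cycle is cancelled has no scheduled primary outcome

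*Combined protocol and SAP*

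**What the plan says.** All references are to the combined protocol and SAP.

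- **Survey dates.** Section 6.2 (Assessments) places survey 1 at the baseline ultrasound, survey 2 on the day of trigger, and the rest at "3 weeks following egg retrieval, 6 weeks following egg retrieval and 12 weeks following egg retrieval if not pregnant". The closing condition concerns pregnancy, not a missing retrieval. Section 6.3.1 (Study Schedule) gives the same anchors.
- **Reminders.** Section 6.3.5 (On Study Visits) runs on the same clock: "At 3- 6- and 12-weeks post retrieval, participants will be contacted by phone and reminded to complete survey number 3, 4 and 5 respectively".
- **Primary outcomes.** Section 5.2.1 lists two: "To compare the mean endometriosis pain score at baseline, 6 and 12 weeks following egg retrieval" and "To evaluate how endometriosis pain scores change throughout controlled ovarian hyperstimulation". The only survey taken during stimulation is survey 2.
- **Randomisation.** Section 6.3.1 puts it at the meeting with the study team, before the baseline ultrasound: "Randomization completed, patient provided medication".
- **Analysis set.** Section 6.4.1 (Statistical Design): "An intention-to-treat analysis of the results will be used, meaning results of the study will be based on the initial treatment assignment".
- **Removal.** Section 6.3.7 lists the reasons for premature discontinuation. A cancelled cycle is not among them.
- **Tests and missing data.** Section 6.4.3.1 names a two-sample t-test or Wilcoxon rank sum test for pain scores. Section 6.4.5 permits multiple imputation if data are missing at random and calls for sensitivity analyses if that is implausible. It does not mention cancelled cycles.

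**The concern.** Trigger and retrieval both come after randomisation, and not every stimulated cycle reaches them. The schedule gives no other date for surveys 2 to 5. Followed as written, a woman with no retrieval stays on study and belongs to the intention-to-treat population, yet she is never asked for the scores that define the first primary outcome. The schedule creates this loss. She may be quite willing to answer an electronic survey at home, but none falls due.

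The primary objective is the effect of ovarian hyperstimulation on symptoms, and a woman cancelled during stimulation has had some of that exposure. If such women are missing from the 6- and 12-week comparison, it describes women who reached retrieval rather than women who were randomised. Pain at a given week cannot be collected afterwards, so the gap has to be closed in the protocol rather than at analysis.

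**Working it through.** **1. Which scores a woman has, by where her cycle ends.**

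| Cycle ends | Baseline | Survey 2 | Surveys 3-5 |
|---|---|---|---|
| Retrieval done | yes | yes | yes |
| After trigger, no retrieval | yes | yes | no date |
| Before trigger | yes | no date | no date |

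The second row can still contribute to the primary outcome on change during stimulation. The third row contributes to neither primary outcome. Section 6.3.6 arranges a post-IVF visit but attaches no survey to it, so it does not fill the gap.

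**2. Reproducing the planned sample size.** Inputs from section 6.4.2: difference 3 VAS points, SD 2.5, power 0.90, 1:1 allocation, dropout 20%. Alpha is 0.05 (section 6.4.3.1). Sidedness is not stated; two-sided is assumed.

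Power comes from the noncentral t distribution with 2n - 2 degrees of freedom and noncentrality 3 / (2.5 × √(2/n)).

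- n = 16 per arm: 3 / (2.5 × √(2/16)) = 3.39, power 0.907. This is the smallest n that reaches 0.90.
- Allowing for dropout: 16 / (1 - 0.20) = 20 per arm, 40 in total. This matches the plan.
- A one-sided test would need 12 per arm by the normal approximation, and 12 / 0.80 = 15 after dropout. That does not match.

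**3. Effect of cancellations on power.** No cancellation rate is given, so 5-15% is an assumed range: 1 to 3 women of 20 per arm. If these come on top of the 20% dropout:

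| Cancelled | Evaluable per arm | Noncentrality | Power |
|---|---|---|---|
| 0% | 20 × 0.80 = 16 | 3.39 | 0.907 |
| 5% | 20 × 0.75 = 15 | 3.29 | 0.887 |
| 10% | 20 × 0.70 = 14 | 3.17 | 0.863 |
| 15% | 20 × 0.65 = 13 | 3.06 | 0.835 |

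If the two losses multiply instead of adding, 5% leaves 20 × 0.80 × 0.95 = 15.2 per arm (power 0.891) and 15% leaves 20 × 0.80 × 0.85 = 13.6 (power 0.853).

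If the 20% already includes cancelled cycles, 16 per arm remain and power stays at 0.907. Section 6.4.2 does not say which is meant.

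**The case against.** The best defence is that the plan nowhere says these women leave the analysis. Section 6.3.7 keeps data collected before a discontinuation, section 6.4.1 analyses by assignment, and section 6.4.5 offers imputation and sensitivity analyses. This stands in part: exclusion is a consequence of the named tests applied to observed scores, not a stated rule. It does not close the gap. Imputation is optional, and a score dated from a retrieval that never took place is undefined rather than merely unobserved. Any imputed value would be borrowed from women who had the procedure.

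A reader might infer that cancellation will differ by arm because providers cannot see estradiol. The document does not support that. Estradiol is withheld in both arms (sections 6.1.3 and 6.1.7), which if anything removes a route by which letrozole could influence decisions. Trigger timing is "Based on routine trigger shot parameters, including mean diameter of largest follicles", and section 2.1.2 reports no effect of letrozole on oocyte or embryo yield. Differential cancellation is possible, but nothing in the document points to it.

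The size can also be called small. Even if 3 of 20 women were lost in one arm only and their pain change differed by 2 points from the rest, that arm's mean would move by 3/20 × 2 = 0.3 points, a tenth of the 3-point target. Both inputs are assumed, so this shows scale only.

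Finally, a survey counted from cancellation does not measure quite the same thing as one counted from retrieval. That is correct, and it is a cost of the fix.

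**Conclusion.** The gap is real and should be closed. As written, a randomised woman with no retrieval has no scheduled 3-, 6- or 12-week score, and one cancelled before trigger has only a baseline score. This conflicts with the commitment to analyse by initial assignment.

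The effect on power is modest and conditional: from about 0.91 to 0.89-0.84 if 5-15% of cycles are cancelled in addition to the 20% dropout, and none if the 20% covers them. In either case the departure from intention-to-treat remains. Its effect on the estimate cannot be sized from the document, which gives neither a cancellation rate nor any sign of a difference between arms.

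Three stronger readings should be avoided: that the protocol excludes cancelled women, that every such woman lacks all post-baseline data, and that the sample size is wrong. The first is not stated, a woman who reached trigger still has survey 2, and the planned 40 reproduces.

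**What to change.** In sections 6.2, 6.3.1 and 6.3.5, add fallback dates:

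- if there is no trigger, survey 2 is completed on the day the cycle is cancelled;
- if there is no retrieval, surveys 3, 4 and 5 are sent 3, 6 and 12 weeks after the cancellation date.

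In section 6.4, state that these women are analysed in their randomised arm, and add a sensitivity analysis limited to women who had a retrieval. The change concerns survey dates and analysis only, not treatment.

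**Cost.** A sentence or two in each section and a date rule in REDCap. The follow-up surveys are already electronic and completed at home, so no visit is added.

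**Downside.** For these few women the score is not strictly post-retrieval. They had neither the retrieval nor the capsule course that follows it, so their time points are not fully comparable with the others. The protocol should say so, and the sensitivity analysis shows how much it matters.

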6.2.1 Efficacy

Letrazole 5mg oral daily has been routinely used in women with estrogen sensitive cancer undergoing controlled ovarian hyperstimulation. It has also been used off-label for many years as a standard treatment for pain related to endometriosis.

6.2.2 Safety/Pregnancy-related policy

Letrazole is contraindicated during female pregnancy because of probable adverse effects on the fetus (FDA pregnancy risk category X). Pregnancy is ruled out in all women undergoing controlled ovarian hyperstimulation prior to starting stimulation medications.

6.2.2.1 Adverse Events Definition and Reporting

Risks and side effects related to the possible use of letrozole include those which are:

Likely

- Flushing
- Mood changes
- Hot flushes
- Bloating

Less Likely

- Headache
- Fatigue
- Insomnia

Rare but serious

- Headache with vision changes
- Blood clot

Patients undergoing controlled ovarian hyperstimulation are monitored every 1-3 days by University of California Center for Reproductive Health providers. During this monitoring patients will be assessed for any possible concerns or side effects of the study medication. All concerns will be recorded and reviewed by the Data Safety and Monitoring Board on a quarterly basis.

6.2.3 Pharmacokinetics (if applicable)

Not applicable.

6.2.4 Biomarkers (if applicable)

Not applicable.

6.3 Study Procedures

Management of participants' ovarian stimulation will be done by their primary doctor based on their knowledge, expertise and established standard of care guidelines. Participants will come to the clinic for transvaginal ultrasound visits to track follicle development, and blood draws will be completed per routine. Serum estradiol levels will be run on all participant blood samples at the end of the study to assure blinding of patients and providers, as discussed in section 6.1.3 above. When follicles are an adequate size, participants will be instructed to take a trigger shot, an injectable hormone medicine that helps to prepare eggs for retrieval. On the day of the egg retrieval procedure, the treating physician will use standard of care transvaginal aspiration to drain all of the visible follicles in order to retrieve eggs. After the egg has been isolated, the excess fluid and cells are usually discarded. We will collect the follicular fluid from the first follicle aspirated in each ovary to perform hormone assays. Throughout the ovarian stimulation process, participants will be asked to complete electronic surveys about symptoms they are experiencing related to their endometriosis.

6.3.1 Study Schedule

M.D. Visit	
 • M.D. to identify patient as potential study participant • M.D. discusses study with patient • M.D. to notify study team if patient interested
Meet Study Team	
 • Discuss study with patient and answer questions • Subject signs study and HIPPA consents • Randomization completed, patient provided medication
Baseline Ultrasound	
 • Completion of survey #1
Stimulation Monitoring	
 • Daily letrozole/placebo starting with first day of stimulation medications • Routine uterine and ovarian ultrasound monitoring every 1-3 days at UCSF CRH • Routine blood draws for hormonal assessment every 1-3 days at UCSF CRH (patients and providers blinded to estradiol levels)
Trigger Shot	
 • Based on routine trigger shot parameters, including mean diameter of largest follicles • Completion of survey #2 • Discontinuation of letrozole/placebo
Oocyte Retrieval	
 • Retrieve all visible follicles • Follicular fluid obtained for hormonal evaluation • Restart letrozole/placebo evening of retrieval and continue daily for 2 weeks
Embryology Lab	
 • Count total number of retrieved oocytes • Count mature oocytes and fertilization rate (if making embryos) • Assess embryo quality using UCSF CRH standard grading criteria

3 Weeks Post Retrieval	
 Completion of survey #3
6 Weeks Post Retrieval	
 Completion of survey #4
12 Weeks Post Retrieval	
 Evaluation of pregnancy status Completion of survey #5
Long-term Follow-up	
 Medical record review for pregnancy outcomes of transferred embryos and additional endometriosis treatment.

6.3.2 Informed Consent

Once an individual is found to qualify for the study, details and all questions will be discussed during the informed consent process. Signed informed consent from the individual will be obtained. The informed consent/permission/assent form covers information about the overall purpose of the study, what the study entails, potential risks, potential benefits to participating individuals and society, the confidentiality of data, and contact information for the Principal Investigator and the IRB.

Once informed consent/permission/assent has been obtained, the research staff will have the form reviewed by a fellow research team member, who will confirm that it is fully and accurately completed before it is filed in a secure location under double-lock when not in use and with restricted access during work hours and/or when unattended.

Consent/Accent/Permission must be obtained within 30 days prior to study entry. If more than 30 days has elapsed since consent/assent/permission was obtained, consent/assent /permission must be verbally reaffirmed on the day of study entry prior to implementing any study activities.

All investigators obtaining consent will be HIPAA and CITI certified in addition to having prior experience in other studies obtaining consent.

6.3.3 Screening

Potential participants will be receiving services at the University of California San Francisco Center for Reproductive Health. Medical providers will identify potential participants and notify the research team. The research team will then recruit participants for the study by speaking with patients face-to-face or by telephone. Information regarding the study will be provided and interest in participation will be assessed.

6.3.4 Recruitment, Enrollment and Retention

Each potential participant identified by Center for Reproductive Health providers will have their medical records reviewed to assess potential eligibility. They will meet with research staff to further discuss the details of the study. If enrollment is desired, consents will be signed, randomization completed and medications dispensed. This will be scheduled to coincide with other necessary clinic visits in preparation for their planned controlled ovarian hyperstimulation cycle.

Patients consented for study participation will have the following information entered on the Study Recruitment Log, which will be maintained in a secure area at the site: name or initials, date of birth, age, and enrollment status. Individuals who were assessed as ineligible for enrollment will have the reasons for ineligibility recorded. Individuals who are approached, but do not consent to participate will also be recorded

Information collected on enrolled participants in the Study Recruitment Log, excluding names or initials and dates of birth, will be entered in the study-specific database.

When study accrual ends, project staff will obliterate all information on the Study Recruitment Log belonging to individuals who did not consent to participate in the study.

6.3.5 On Study Visits

Enrollment:

As described above, participants will be identified by their primary provider as a possible study candidate. The research team will be notified, review the patient's chart for eligibility and meet with the patient to further discuss the study. If the patient desires enrollment, consents will be signed, randomization will be completed and medication will be dispensed to the patient.

Baseline Ultrasound:

Participants will present for their routine baseline ultrasound as part of their controlled ovarian hyperstimulation protocol. This is typically done on cycle day 2, prior to the initiation of gonadotropin medications and study medication. Participants will also complete survey #1 within 24 hours of this visit. The survey can be completed on a clinic provided electronic device at the time of their visit or at home electronically via a secure RedCap portal.

Stimulation Monitoring:

Patients will take their study drug and gonadotropins daily as advised by their primary team. They will present for monitoring every 1-3 days at the University of San Francisco Center for Reproductive Health. At each visit, patient symptoms will be evaluated and as previously discussed, any concern for side effects from the study drug will be reported to the research team.

Trigger Shot:

Per routine trigger shot parameters, including mean diameter of largest follicles, the participant will be instructed when to administer their trigger shot. Participants will be instructed to complete survey #2 within 24 hours of this visit. The survey can be completed on a clinic provided electronic devise at the time of their visit or at home electronically via a secure RedCap portal. Participants will also be advised to discontinue their study medication until the night of their retrieval.

Oocyte Retrieval:

Participants will undergo a standard egg retrieval procedure at the University of California Center for Reproductive Health procedure suite. Follicular fluid from the first follicle aspirated in each ovary will be collected to perform hormone assays. The embryology lab

will complete their routine evaluation of the retrieved oocytes as well as the fertilization rate and embryo quality. On the day of retrieval, participants will be reminded to restart their study medication and continue to take it daily for two weeks.

Post Retrieval Surveys:

At 3- 6- and 12-weeks post retrieval, participants will be contacted by phone and reminded to complete survey number 3, 4 and 5 respectively. These surveys will be completed at home electronically via a secure RedCap portal.

Long Term Follow Up:

After completion of survey 5 participants will not be contacted again about the study. Their chart will be periodically reviewed to assess pregnancy outcomes from the controlled ovarian hyperstimulation cycle. Treatments they receive related to their diagnosis of endometriosis will also be reviewed.

6.3.6 End of Study and Follow-up

Regardless of whether participants have completed ovarian stimulation with letrozole or placebo, they will be scheduled for a post-IVF visit with their treating physician to discuss the outcome. This visit is a standard of care procedures for all IVF patients. The participant's nurse will schedule this visit.

